The power to detect relative risks of 1.5 and 2 was determined for each of the study outcomes for each individual country ([Table 7](#)) and for the final random-effects meta-analysis ([Table 8](#)). For the single-country analyses, power computations were based on HRs derived from Cox models. For the meta-analysis, simulations were used to estimate country-level HRs which were then entered into random-effects meta-analysis models as described in [Section 8.7.1.4](#). All power computations were based on the expected number of individuals exposed to empagliflozin eligible for inclusion in the study and the observed country-level IRs of urinary tract cancers, bladder cancer and renal cancer in the study population as reported in the 5th Interim Report. The expected averages of follow-up time were 2.4 years for UK CPRD, 2.2 for Sweden, and 2.4 for Finland, as reported in the 5th Interim Report. Matching ratios of empagliflozin initiators to initiators of DPP-4 inhibitors were fixed at 1:3 for UK CPRD, 1:1 for Sweden, and 1:2 for Finland. These are the highest achievable matching ratios given expected patient numbers. For computing the meta-analysis power, these assumptions were used to simulate for each country separately individual level time-to-event data from each drug cohort following an exponential distribution given the expected number of empagliflozin initiators, the expected matching ratio, the observed incidence rates as the baseline rate in the DPP-4 cohort. The hazard ratio for each simulation run was determined by drawing from a normal distribution with a mean of the natural logarithm of the target hazard ratio (1.5 or 2.0) and a standard deviation of 0.1. These individual time-to-event data were then entered into a Cox proportional hazard model for each country to compute a simulated hazard ratio. For each simulation, the country-level hazard ratios were entered into a random-effects meta-analysis level, and the resulting p-value of the pooled estimate was retained. Simulations were run 500 times and power was computed as the proportion of simulations for which the p-value of the pooled estimate was inferior to 0.5.

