8.7.1.4 Comparative analyses

Relative risks (HRs) for the defined outcomes will be estimated using Cox models with time-varying covariates if model pre-requisites are fulfilled. HRs will be presented along with 95% CIs.

The Cox models will include the exposure and the comparator group within the model. This will account for multiple testing and for retaining same variables in variable selection (see [Section 8.7.1.6](#)). The models are defined in terms of covariates adjusted for in addition to the primary exposure: (i) baseline model with covariates adjusted for with values at index date (ii) model with time-dependent covariates wherein change in covariates over the follow-up period after index date are also incorporated into the model.

Country-specific analysis:

The country-specific Cox models will be fit with single-country level datasets. The analyses will use datasets from the UK, Sweden, and Finland, separately.

Meta-analysis:

Country-level effect sizes will be pooled using meta-analysis models to compute pooled effect size estimates. Prior to conducting meta-analyses, heterogeneity across the countries in terms of study design and conduct will be assessed. Specifically, the variability in population characteristics (including data availability), propensity score matching variables as well as propensity score balance will be examined.

Meta-analyses will be carried out for analyses where the country-level effect size is available for all three study countries. Pooled effect sizes will be estimated using random-effects models. The inverse-variance method will be used where appropriate.

Statistical heterogeneity between country-level estimates will be assessed using:

- Cochran's Q test
- I^2 statistic and its 95% CI
- The τ^2 statistic and its 95% CI

For each meta-analysis model, results will be presented in a forest plot including at least the following data:

- Data source.
- Effect size and 95% CI for each study included in the analysis (on a log scale).
- The weights allocated to each study.
- The combined estimated effect size with 95% CI (on a log scale) for the random-effects model.
- Value of Cochran's Q statistic, with the number of degrees of freedom and p-value.
- The proportion of variability explained by heterogeneity (I^2).
- The between-study variance τ^2 .

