- Ever exposed to thiazolidinediones (as defined in Table 14)
- Ever exposed to sulfonylureas (as defined in Table 14)

HRs estimated using the adjusted model with time-dependent covariates will be presented along with 95% CIs. A table template for the result is given in Table 25. Analysis will be performed and model adjustment will be applied separately for each country.

Adjusted HRs with 95% CIs will be collected from all study countries to carry out meta-analyses as described in Section 6.7.3.2. Results will be reported as in Figure 8.

Handling of model convergence failure

For outcomes with a small number of events, convergence failure of multivariable Cox PH regression model may happen if there are no events for a particular combination of covariate values. Thus, a minimum of 5 outcome events per category of a variable is required for it to be included in the Cox model. In case of persisting model convergence failure while meeting this minimum requirement, the included covariates will be removed sequentially based on the rank of their PS standardised differences. The covariate with the smallest standardised difference will be removed iteratively until the model converges. In case of ties in selection, the choice is made randomly. The removed covariates will be reported along with the HR estimates.

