6.7.3. META-ANALYSES

Meta-analyses will be carried out when there is no relevant heterogeneity of variable definitions and effect size of outcomes with respect to primary exposures among country-specific analyses. Country-level effect-sizes will be pooled using meta-analysis models to compute pooled effect-size estimates.

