6.7.3.2. META-ANALYSIS OF COMPARATIVE ANALYSIS

Meta-analyses will combine the estimates of adjusted HRs across countries using the inverse-variance method. Log-transformed HRs and their standard errors will be collected to calculate pooled HR estimates using random-effects models. Pooled HRs and their 95% CI will be reported using forest plots. In a sensitivity analysis, pooled HRs will be estimated using fixed-effect models.

Between-study heterogeneity

Prior to conducting meta-analyses, heterogeneity across the countries in terms of study design and conduct will be assessed. Specifically, the variability in population characteristics (including data availability), in pre- and post- PS matching balance in baseline characteristics between cohorts, as well as in observed incidence rates will be examined. If needed, changes in study population selection criteria or other analysis parameters will be considered to reduce such heterogeneity.

Statistical heterogeneity between country-level estimates will be estimated using Higgins' and Thompson's I^2 [9] and the moment-based estimate of τ^2 .

Both I^2 and τ^2 are derived using Cochran's Q statistic defined as

$$Q = \sum_{k=1}^K w_k \left(\hat{\theta}_k - \frac{\sum_{k=1}^K w_k \hat{\theta}_k}{\sum_{k=1}^K w_k} \right)^2; w_k = \frac{1}{s_k^2}$$

where $\hat{\theta}_k$ denotes the log-transformed per-country HR estimate, s_k^2 its variance, w_k the corresponding weight from the country-level study k calculated as the inverse of variance s_k^2 .

I^2 statistic

I^2 is the percentage of variability in the treatment estimates which is attributable to heterogeneity between studies rather than to sampling error. I^2 is formulated as

$$I^2 = \max \left\{ 0, 1 - \frac{Q - K - 1}{Q} \right\}$$

where Q is Cochran's Q statistic and K is the number of the per-country studies.

I^2 and its 95% CIs are used to assess the importance of between study heterogeneity as follows:

- 0% to 40%: might not be important
- 30% to 60%: may represent moderate heterogeneity
- 50% to 90%: may represent substantial heterogeneity
- 75% to 100%: considerable heterogeneity

Proprietary confidential information © 2024 Boehringer Ingelheim International GmbH or one or more of its affiliated companies

I^2 is sensitive to the precision of the included studies, with higher I^2 associated with increased precision in individual studies.

τ^2 statistic

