Kaplan-Meier survival probability plots	Using matched cohorts Country specific analysis (9 figures, 3 outcomes x 3 countries)	As treated exposure definition	Main outcomes- Table 8	Figure 6
Primary objectives: Comparative analysis				
Hazard ratio estimates using crude model	Using matched cohorts Country specific analysis (18 tables, 2 cohorts x 3 outcomes x 3 countries)	As treated exposure definition	Main outcomes- Table 8	Table 23

Analysis	Details	Exposure definition	Outcomes	Template
Meta-analysis of crude HR estimates	Using adjusted HR estimates and 95% CIs from all study countries (2 cohorts: 6 figures, 3 outcomes)	As treated exposure definition	Main outcomes- Table 8	Figure 8
Hazard ratio estimates using the base model	Using matched cohorts Country specific analysis (18 tables, 2 cohorts x 3 outcomes x 3 countries)	As treated exposure definition	Main outcomes- Table 8	Table 23
Meta-analysis of HR estimates using the base model	Using adjusted HR estimates and 95% CIs from all study countries (2 cohorts: 6 figures, 3 outcomes)	As treated exposure definition	Main outcomes- Table 8	Figure 8
Hazard ratio estimates using the adjusted model	Using matched cohorts Country specific analysis (18 tables, 2 cohorts x 3 outcomes x 3 countries)	As treated exposure definition	Main outcomes- Table 8	Table 25
Meta-analysis of adjusted HR estimates	Using adjusted HR estimates and 95% CIs from all study countries (2 cohorts: 6 figures, 3 outcomes)	As treated exposure definition	Main outcomes- Table 8	Figure 8
Stratified analysis				
Hazard ratio estimates using adjusted model	Using matched cohorts Stratified by treatment complexity at index. (27 tables, 3 outcomes x 3 strata by treatment complexity at index x 3 countries)	As treated exposure definition	Main outcomes- Table 8	Table 25

Analysis	Details	Exposure definition	Outcomes	Template
Hazard ratio estimates using adjusted model	
Using matched cohorts
 
Stratified by PS quartiles at index.
 
(36 tables, 3 outcomes x 4 strata by propensity score quartiles x 3 countries)
	As treated exposure definition	Main outcomes- Table 8	Table 25
Hazard ratio estimates using adjusted model	
Using matched cohorts
 
Stratified by age category at index.
 
(63 tables, 3 outcomes x 7 strata by age category x 3 countries)
	As treated exposure definition	Main outcomes- Table 8	Table 25

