DPP-4 inhibitors	reference	reference	reference	reference
Empagliflozin	x.XXX	x.XXX	x.XXX	x.XXX

Proprietary confidential information © 2024 Boehringer Ingelheim International GmbH or one or more of its affiliated companies

Table 43 Adjusted hazard ratios for [Outcome Name] incidence estimated using the Cox proportional hazards model in the UK matched cohort after adding CPRD database as a stratification variable. The table shows the hazard ratios (HRs) using the base model with the corresponding 95% CI and p-value—As treated exposure definition.

Variables	Hazard ratio	Lower 95% CI	Upper 95% CI	P-value
AT exposure				
DPP-4 inhibitors	reference	reference	reference	reference
Empagliflozin	x.XXX	x.XXX	x.XXX	x.XXX

[figure not shown]
Proprietary confidential information © 2024 Boehringer Ingelheim International GmbH or one or more of its affiliated companies

Table 44 Adjusted hazard ratios for [Outcome Name] incidence estimated using the Cox proportional hazards model in the [Study country] matched cohort after adding CPRD database as a stratification variable. The table shows the hazard ratios (HRs) using the adjusted model with the corresponding 95% CI and p-value—As treated exposure definition.

Variables	Hazard ratio	Lower 95% CI	Upper 95% CI	P-value
AT exposure				
DPP-4 inhibitors	reference	reference	reference	reference
Empagliflozin	x.xxx	x.xxx	x.xxx	x.xxx

Proprietary confidential information © 2024 Boehringer Ingelheim International GmbH or one or more of its affiliated companies

Figure 8. Meta-analysis of [hazard/odds] ratios of [outcome] for the [analysis type] using a random-effects model

[figure not shown]

Random effects model:

Heterogeneity: Q (df: N) = N, p-value N, $I^2 = N\% [N\%, N\%]$, $\tau^2 = N [N, N]$.

Proprietary confidential information © 2024 Boehringer Ingelheim International GmbH or one or more of its affiliated companies

Figure 9. Meta-analysis of hazard ratios of [outcome] for the as-treated analysis of empagliflozin users vs DPP-4 users using a fixed-effect model (sensitivity analysis)

[figure not shown]

Fixed effects model:

Overall effect: Z = N, p-value N.

[figure not shown]
Proprietary confidential information © 2024 Boehringer Ingelheim International GmbH or one or more of its affiliated companies

Figure 10. Average number of diabetes-related healthcare visits per patient recorded in the source population for study years 2015-[end of study year]

[figure not shown]

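### SAP 6.7.3 makes pooling depend on undefined agreement of effect sizes, prints I² upside down, and lets selection criteria change after incidence rates are seen

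*SAP*

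**What the plan says.** **Pooling.** SAP 6.7.3 opens with a condition: "Meta-analyses will be carried out when there is no relevant heterogeneity of variable definitions and effect size of outcomes with respect to primary exposures". It does not define relevance. Protocol 8.7.1.4 has a different rule: "Meta-analyses will be carried out for analyses where the country-level effect size is available for all three study countries". Its response to high heterogeneity is to review the country analyses, discuss likely sources and add a fixed-effect sensitivity analysis. Elsewhere the SAP schedules pooling without condition. Section 6.7.2 says "Adjusted HRs with 95% CIs will be collected from all study countries to carry out meta-analyses as described in Section 6.7.3.2", and Table 16 in section 6.10 lists the meta-analyses as "Using adjusted HR estimates and 95% CIs from all study countries". The power simulation in Protocol 8.5 also pools every time: "For each simulation, the country-level hazard ratios were entered into a random-effects meta-analysis level, and the resulting p-value of the pooled estimate was retained".

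**I².** SAP 6.7.3.2 says that I² "is the percentage of variability in the treatment estimates which is attributable to heterogeneity between studies rather than to sampling error" and grades it in overlapping bands, the top one being "75% to 100%: considerable heterogeneity". The formula printed beside this is I² = max{0, 1 − (Q − K − 1)/Q}. The bands are not linked to the decision to pool. The Figure 8 template also shows "Heterogeneity: Q (df: N) = N, p-value N".

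**Changes before pooling.** SAP 6.7.3.2 has the team examine population characteristics, matching balance and observed incidence rates. It then lets them consider altering selection criteria or other analysis parameters to reduce heterogeneity. SAP section 10 requires approval of every revision and documentation of major ones.

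**The concern.** These are three independent defects.

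(a) The existence of the primary pooled estimate can depend on the observed country hazard ratios, judged by a rule nobody has written down. A random-effects model is chosen because true effects may differ between countries, so requiring agreement first works against it. Without pooling, power is poor: for bladder cancer at HR 1.5, Protocol Table 7 gives 43.1%, 66.6% and 54.3% by country, against 84.0% pooled in Table 8.

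(b) If coded as printed, I² would label homogeneous results as heterogeneous and the reverse.

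(c) Incidence rates are outcome data, and the SAP's Table 22 template breaks them down by exposure group. Changing the population after seeing them, without a duty to report the planned analysis, weakens pre-specification in a regulator-required safety study.

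**Working it through.** **(a) Size of the pooling condition**

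Inputs: numbers of initiators, matching ratios, incidence rates and mean follow-up from the notes to Protocol Tables 7 and 8; SD of 0.1 for the log hazard ratio from Protocol 8.5; the 6-month lag from Protocol 8.3.5. Subtracting the lag from mean follow-up is my assumption. Expected DPP-4 events are N × ratio × years × rate; expected empagliflozin events are N × years × rate × HR. Var(log HR) = 1/d1 + 1/d0.

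Urinary tract cancer at HR 1.5:

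| Country | N | Ratio | Years at risk | Rate per 100,000 | Empagliflozin events | DPP-4 events | Var(log HR) |
|---|---|---|---|---|---|---|---|
| UK | 16,360 | 1:3 | 2.4 − 0.5 = 1.9 | 111.5 | 52.0 | 104.0 | 0.0289 |
| Sweden | 32,334 | 1:1 | 2.2 − 0.5 = 1.7 | 164.5 | 135.6 | 90.4 | 0.0184 |
| Finland | 18,269 | 1:2 | 2.4 − 0.5 = 1.9 | 161.5 | 84.1 | 112.1 | 0.0208 |

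I ran 400,000 simulations per setting with Poisson events, a separate log HR per country drawn from N(ln HR, 0.1), DerSimonian-Laird pooling, two-sided 5%, and the correct I² = max{0, (Q − 2)/Q}. (Protocol 8.5 prints the significance cut-off as 0.5. That would give about 96% to 100% power everywhere, so Table 8 must have used 0.05.) The SAP gives no cut-off for pooling, so several are shown.

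| Outcome, HR | Table 8 power | Reproduced | Withheld, I² ≥ 75% | Withheld, Q p < 0.10 | Withheld, I² ≥ 50% | Withheld, I² ≥ 40% | Pooled and significant, 75% cut | Pooled and significant, 50% cut |
|---|---|---|---|---|---|---|---|---|
| Urinary tract, 1.5 | 93.6% | 93.2% | 6% | 20% | 25% | 32% | 90% | 74% |
| Bladder, 1.5 | 84.0% | 83.3% | 4% | 16% | 20% | 27% | 82% | 72% |
| Renal, 2.0 | 97.0% | 97.5% | 3% | 14% | 18% | 24% | 95% | 82% |

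Without subtracting the lag, urinary tract power is 95.8%, which fits Table 8 less well. Withholding is then 7.6%, 27.9% and 34.4% at the 75%, 50% and 40% cuts, and the chance of a pooled, significant result at the 50% cut is 71.6%.

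If true hazard ratios are identical in all countries, Q follows chi-square on 2 df and P(Q ≥ q) = exp(−q/2). I² ≥ 75%, 50% and 40% correspond to Q ≥ 8, 4 and 3.33:

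- exp(−4) = 1.8%
- exp(−2) = 13.5%
- exp(−1.67) = 18.9%

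These lower figures also apply if Protocol 8.5 means one draw per run shared by all countries, which its wording permits. Power hardly distinguishes the two readings: without the lag, renal cancer at HR 1.5 gives 75.2% with separate draws and 74.8% with a shared draw.

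**(b) The I² formula**

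1 − (Q − K − 1)/Q = (K + 1)/Q, which is 4/Q for K = 3.

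| Q | Printed: 4/Q | Correct: max{0, (Q − 2)/Q} |
|---|---|---|
| 1 | 400% | 0% |
| 4 | 100% | 50% |
| 8 | 50% | 75% |
| 20 | 20% | 90% |

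Under homogeneity the printed form reads 75% or more when Q ≤ 5.33, with probability 1 − exp(−2.67) = 0.93. It exceeds 100% when Q < 4, with probability 1 − exp(−2) = 0.86. Two things are wrong: the leading 1 − and the missing brackets around K − 1. Removing only the first gives (Q − 4)/Q; adding only the brackets gives 2/Q. Neither is right. The τ² formula in the same section has the correct numerator, Q − (K − 1).

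**(c) The texts side by side**

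Protocol 8.7.1.4 lists population characteristics, matching variables and balance for review before pooling. It does not list incidence rates and offers no change of criteria. SAP 6.7.3.2 adds both. SAP section 10 covers approval and documentation, but no text says that the pre-specified analysis stays primary or is reported alongside. This cannot be sized in advance.

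**The case against.** **On (a).** The working parts of the SAP already point to unconditional pooling: 6.7.2 refers to 6.7.3.2 rather than to the opening condition, Table 16 is unconditional, and I² is graded up to its highest band on a plot of pooled results. That supports the repair, but it leaves the SAP contradicting itself. The SAP says it follows protocol version 6.0, whereas the meta-analysis description came with version 7.0. However, the SAP was revised on 26 July 2022, after version 7.0 of 28 June 2022, and adopted that version's CPRD Aurum data and extended UK period. Protocol 8.7.1.4 leaves further detail on heterogeneity to the SAP, but it already fixes when to pool. The fair point is that every cut-off here is mine. At the SAP's own top band the loss is small, and country estimates are reported either way.

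**On (b).** I² is defined correctly in words with a reference, the analysis is in R with independent checking, and a value of 400% would be noticed. Harm arises only if the printed expression is hand-coded. The text was machine-read, so check the PDF; the neighbouring Q and τ² formulas came through intact.

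**On (c).** Protocol 8.8 and SAP section 10 rule out silent changes, country hazard ratios are not named as a trigger, and overall country rates were already known from the fifth interim report. This limits the concern. It does not supply the missing duty to keep the planned analysis.

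**Conclusion.** All three points hold, and (a) carries most weight. As written, the SAP can withhold the primary pooled estimate under an undefined rule, against the protocol and its own list of analyses. How often depends on the cut-off and the true heterogeneity: from about 2% (75% cut, identical true effects) to about a third (40% cut, SD 0.1, urinary tract). Stated power makes no allowance for this. These figures rest on my cut-offs, on the lag subtraction and, for the higher values, on country-specific draws; the identical-effects figures need only the chi-square approximation. Point (b) is a plain formula error that could misgrade heterogeneity in the report but changes no pooled hazard ratio or interval. Point (c) is a weaker safeguard issue, partly covered by change control. Together they should be fixed before the analysis is run.

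**What to change.** 1. In SAP 6.7.3, replace the effect-size condition with the protocol's rule: random-effects pooling wherever all three country estimates exist, always reporting Q, I² and τ². Keep the review of variable definitions and data availability as a description of comparability.
2. In SAP 6.7.3.2, print I² = max{0, (Q − (K − 1))/Q}.
3. In the same section, state that the pre-specified population and parameters remain the primary analysis, and that any version altered after seeing the data is reported only as a labelled post-hoc sensitivity analysis.

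The cost is three text edits in the SAP, with no new data and no added analysis.

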6.7.3.1. META-ANALYSIS OF DESCRIPTIVE ANALYSES

Pooled incidence rates

For each outcome, the aggregated number of events and person-time at risk will be collected from all study countries to estimate the pooled IRs and their 95% CIs.

The pooled IRs for all K countries will be estimated as

$$IR_{pooled} = \frac{\sum_{k=1}^K x_k}{\sum_{k=1}^K t_k}$$

where x_k and t_k are the number of events and the person-time at risk in each country k .

95% CIs will be estimated using Poisson regression and reported similarly using Table 22.

